7.2 Lost to follow-up

A patient will be considered potentially lost to follow-up if he or she fails to return for scheduled visits and is unable to be contacted by the study site.

The following actions must be taken if a patient fails to return to the clinic for a required study visit:

- The site must attempt to contact the patient and reschedule the missed visit as soon as possible and counsel the patient on the importance of maintaining the assigned visit schedule.
- Before a patient is deemed lost to follow-up, the Investigator or designee must make every effort to regain contact with the patient or next of kin by eg, repeat telephone calls, certified letter to the patient's last known mailing address or local equivalent methods. These contact attempts should be documented in the patient's medical record.
- Efforts to reach the patient should continue until the end of the study. Should the patient be unreachable at the end of the study the patient should be considered lost to follow-up with unknown vital status at end of study and censored at latest follow-up contact.

7.3 Withdrawal from the study

A patient may withdraw from the study (eg, withdraw consent), at any time (study treatment **and** assessments) at his/her own request, without prejudice to further treatment.

A patient who considers withdrawing from the study must be informed by the Investigator about modified follow-up options (eg, telephone contact, a contact with a relative or treating physician, or information from medical records). If the patient withdraws consent for disclosure of future information, the Sponsor may retain and continue to use any data collected before such a withdrawal of consent.

If a patient withdraws from the study, he/she may request destruction of any samples taken, and the Investigator must document this in the site study records.

A patient who withdraws consent will always be asked about the reason(s) and the presence of any AE. The Investigator will follow up patients as medically indicated.

AstraZeneca or its delegate will request Investigators to collect information on patients' vital status (dead or alive; date of death when applicable) at the end of the study from publicly available sources, in accordance with local regulations. Knowledge of the vital status at study end in all patients is crucial for the integrity of the study.

See SoA for data to be collected at the time of study discontinuation and follow-up and for any further evaluations that need to be completed. All study treatment should be returned by the patient.

8 STUDY ASSESSMENTS AND PROCEDURES

Study procedures and their timing are summarised in the SoA.

The Investigator will ensure that data are recorded on the CRF. The Web Based Data Capture system will be used for data collection and query handling.

The Investigator ensures the accuracy, completeness and timeliness of the data recorded and of the provision of answers to data queries according to the Clinical Study Agreement. The Investigator will sign the completed CRF. A copy of the completed CRF will be archived at the study site.

Immediate safety concerns should be discussed with the Sponsor immediately upon occurrence or awareness to determine if the patient should continue or discontinue study treatment.

Adherence to the study design requirements, including those specified in the SoA, is essential and required for study conduct.

All screening evaluations must be completed and reviewed to confirm that potential patients meet all eligibility criteria. The Investigator will maintain a screening log to record details of all patients screened and to confirm eligibility or record reasons for screening failure, as applicable.

Procedures conducted as part of the patient's routine clinical management (eg, blood count) and obtained before signing of the ICF may be utilised for screening or baseline purposes provided the procedures met the protocol-specified criteria and were performed within the time frame defined in the SoA.

The number of samples taken, as well as the volume required for each analysis, may be changed during the study as emerging data become available. However, the estimated total volume of blood that will be drawn from each patient in this study during screening and the first cycle of treatment will not exceed approximately 350 mL (over a 1 month period). Any additional requirements are specified within the relevant section of Combination Module 1. Safety laboratory assessments will be performed locally at each centre's laboratory by means of their established methods. Therefore, the number of samples/blood volumes is patient to site-specific change.

8.1 Efficacy assessments

8.1.1 Tumour assessments by CT or MRI

RECIST 1.1 guidelines for measurable and non-measurable TLs and non-target lesions (NTLs) and the objective tumour response criteria are presented in Appendix H of this protocol.

At baseline, the imaging modalities used for assessment should be contrast enhanced computed tomography (CT) (magnetic resonance imaging [MRI] where CT is contraindicated) scans of the brain, chest, abdomen and pelvis (including liver and adrenal glands) and should encompass all areas of known predilection for metastases in the disease under evaluation, and should additionally investigate areas that may be involved based on signs and symptoms of individual patients. Follow-up CT or MRI assessments will cover chest, abdomen and pelvis with any other regions imaged at baseline where disease was present. Any other sites at which new disease is suspected should also be appropriately imaged. A CT/MRI scan of the brain should be performed in all patients at the main screen.

Radiological examinations performed in the conduct of this study should be retained at site as source data. All treatment decisions will be based on site assessment of scans. Baseline radiological assessments should be performed no more than 28 days before the start of study treatment, and ideally should be performed as close as possible to the start of study treatment. Scans obtained as part of standard clinical practice, prior to informed consent, but within the 28-day period are acceptable. The radiological confirmatory scans should be performed no less than 4 weeks after the prior assessment of tumour and preferably at the next scheduled visit (in the absence of clinically significant deterioration).

The methods of assessment used at baseline should be used at each subsequent follow-up assessment through to objective confirmed radiological disease progression, as defined by

RECIST 1.1 and as determined by the Investigator. Tumour assessments should be performed every 8 weeks (2 cycles) (\pm 1 week) or earlier, if disease progression is suspected. If a patient discontinues treatment (and/or receives a subsequent cancer therapy) prior to progression then the patient should continue to be followed (unless they withdraw consent) until confirmed objective disease progression, as defined by RECIST 1.1. Scans confirming progression should not be conducted within 1 week after a progression biopsy to allow for reduction in inflammation.

If scans are performed outside of scheduled visit window interval and the patient has not progressed, every attempt should be made to perform the subsequent scans at their scheduled visits whilst the patient remains on study treatment. If the patient interrupts treatment or incurs a treatment delay, scans should continue to occur at the protocol-defined frequency.

It is important to follow the assessment schedule as closely as possible. Please refer to the SoA.

8.1.2 Tumour evaluation

Categorisation of objective tumour response assessment will be based on the RECIST 1.1 criteria of response: CR, PR, and SD (see Appendix H). The CR and PR will need to be confirmed. In addition, the objective tumour response assessment will also be assessed for exploratory analysis on a modified RECIST 1.1 (mRECIST) criteria considering progression only when confirmed. The mRECIST will not be used for the Core Module or Combination Module 1, but will be used if any immune oncology (IO) combination modules are added to the study in the future. TL progression will be calculated in comparison to when the tumour burden was at a minimum (ie, smallest sum of diameters previously recorded on study). In the absence of progression, tumour response will be calculated in comparison to the pre-dose tumour measurements obtained before starting treatment.

If the Investigator is in doubt as to whether progression has occurred, particularly with response to NTLs or the appearance of a new lesion, it is advisable to continue treatment until the Investigator reassesses the patient's status at the next scheduled assessment (confirmation) or sooner if clinically indicated.

To achieve 'unequivocal progression' based on non-target disease, there must be an overall level of substantial worsening in non-target disease such that, even in presence of SD or PR in target disease, the overall tumour burden has increased sufficiently to merit discontinuation of therapy. A modest increase in the size of 1 or more NTLs is usually not sufficient to qualify for unequivocal disease progression status.

If repeated scans confirm progression, then the date of the initial scan should be declared as the date of progression. All RECIST assessment images will be reviewed at site. Duplicates

may be collected and stored by an AstraZeneca appointed representative, and sent for independent central RECIST review, if deemed appropriate.

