A visit response of CR is defined when all TLs and NTLs present at baseline have disappeared (with the exception of lymph nodes which must be <10mm to be considered non pathological) and no new lesions have developed since baseline. A visit response of PR is defined when the sum of diameters of the TLs has decreased by 30% or more compared to baseline (with no evidence of progression) and the NTLs are at least stable with no evidence of new lesions.

In the case of SD, measurements should have met the SD criteria at least once after the study start.

When the Investigator reassesses the progression of the patient at a later date, the date of the initial scan should be declared as the date of progression if the repeat scans confirm progression.

Overall Survival

Overall survival is defined as the time from first dose of any study treatment at Cycle 1 until death due to any cause regardless of whether the patient withdraws from study treatment or receives another anti-cancer therapy (ie, date of death or censoring – date of first dose + 1). Any patient not known to have died at the time of analysis will be censored based on the last recorded date on which the patient was known to be alive.

Survival calls will be made in the week following the date of DCO for the analysis, and if patients are confirmed to be alive or if the death date is after the DCO date these patients will be censored at the date of DCO.

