To achieve 'unequivocal progression' on the basis of NTLs, there must be an overall level of substantial worsening in non-target disease such that, even in presence of SD or PR in TLs, the overall tumour burden has increased sufficiently to merit discontinuation of therapy. A modest 'increase' in the size of 1 or more NTLs is usually not sufficient to qualify for unequivocal progression status.

New Lesions

Details of any new lesions will also be recorded with the date of assessment. The presence of 1 or more new lesions is assessed as progression.

A lesion identified at a follow-up assessment in an anatomical location that was not scanned at baseline is considered a new lesion and will indicate disease progression.

The finding of a new lesion should be unequivocal: ie, not attributable to differences in scanning technique, change in imaging modality or findings thought to represent something other than tumour.

If a new lesion is equivocal, for example because of its small size, the treatment and tumour assessments should be continued until the new lesion has been confirmed. If repeat scans confirm there is a new lesion, then the progression date should be declared using the date of the initial scan.

Symptomatic Deterioration

Symptomatic deterioration is not a descriptor of an objective response: it is a reason for stopping study therapy.

Patients with 'symptomatic deterioration' requiring discontinuation of study treatment without objective evidence of disease progression at that time will undergo no further tumour

assessments in this study. Tumour response data for such patients will be censored at the date of their last RECIST assessment.

Evaluation of Overall Visit Response and Best Overall Response

The overall visit response will be derived using the algorithm shown in Table 4.

		NT T •	0 "
Target lesions	Non-Target lesions	New Lesions	Overall response
CR	CR	No	CR
CR	NA	No	CR
NA	CR	No	CR
CR	Non-CR/Non-progressive disease	No	PR
CR	NE	No	PR
PR	Non- progressive disease or NE	No	PR
SD	Non- progressive disease or NE	No	SD
NA	Non-CR/Non- progressive disease	No	SD (Non-CR/non- progressive disease)
NE	Non- progressive disease or NE	No	NE
NA	NE	No	NE
PD	Any	Yes or No	progressive disease
Any	progressive disease	Yes or No	progressive disease
Any	Any	Yes	progressive disease

Table 4Overall Visit Response

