3.2.2 Secondary Outcome Variables

3.2.2.1 Calculation or derivation of tumour response variables

3.2.2.1.1 RECIST visit responses

For all patients, the RECIST tumour response data will be used to determine each patient's visit response according to RECIST version 1.1. It will also be used to determine if and when a patient has progressed in accordance with RECIST and also their best objective response to study treatment.

Baseline radiological tumour assessments are to be performed no more than 28 days before the first dose/administration of study medication on cycle 1, day 1 and ideally as close as possible to the start of study treatment. Tumour assessments are then performed every 8 weeks (± 1 week) following start of study treatment on cycle 1, day 1 until confirmed disease progression.

If an unscheduled assessment is performed, and the patient has not progressed, every attempt should be made to perform the subsequent assessments at their scheduled visits. This schedule is to be followed in order to minimise any unintentional bias caused by some patients being assessed at a different frequency than other patients.

From the investigator's review of the imaging scans, the RECIST tumour response data will be used to determine each patient's visit response according to RECIST version 1.1. At each visit, patients will be programmatically assigned a RECIST 1.1 visit response of complete response (CR), partial response (PR), stable disease (SD) or partial disease (PD) (see [Table](#)), using the information from target lesions (TLs), non-target lesions (NTLs) and new lesions and depending on the status of their disease compared with baseline and previous assessments. If a patient has had a tumour assessment which cannot be evaluated, then the patient will be assigned a visit response of not evaluable (NE) (unless there is evidence of progression in which case the response will be assigned as PD).

RECIST outcomes (i.e. PFS, ORR etc.) will be calculated programmatically for the site investigator data from the overall visit responses.

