If a TL splits in two, then the LDs of the split lesions should be summed and reported as the LD for the lesion that split.

Lesions that merge

If two TLs merge, then the LD of the merged lesion should be recorded for one of the TL sizes and the other TL size should be recorded as 0cm.

Change in method of assessment of TLs

CT, MRI and clinical examination are the only methods of assessment that can be used within a trial, with CT and MRI being the preferred methods and clinical examination only used in special cases. If a

change in method of assessment occurs between CT and MRI this will be considered acceptable and no adjustment within the programming is needed.

If a change in method involves clinical examination (e.g. CT changes to clinical examination or vice versa), any affected lesions should be treated as missing. The TL visit response may still be evaluable if the number of missing TL measurements at a visit is $\leq 1/3$ of the total number of TLs.

Non-Target Lesions (NTLs) and new lesions – site investigator data

At each visit, the investigator should record an overall assessment of the NTL response. This section provides the definitions of the criteria used to determine and record overall response for NTL at the investigational site at each visit.

NTL response will be derived based on the Investigator's overall assessment of NTLs as described in [Table 2](#).

To achieve 'unequivocal progression' on the basis of NTLs, there must be an overall level of substantial worsening in non-target disease such that, even in the presence of SD or PR in TLs, the overall tumour burden has increased sufficiently to merit a determination of disease progression. A modest 'increase' in the size of one or more NTLs is usually not sufficient to qualify for unequivocal progression status.

Details of any new lesions will also be recorded with the date of assessment. The presence of one or more new lesions is assessed as progression.

A lesion identified at a follow up assessment in an anatomical location that was not scanned at baseline is considered a new lesion and will indicate disease progression.

The finding of a new lesion should be unequivocal: i.e. not attributable to differences in scanning technique, change in imaging modality or findings thought to represent something other than tumour.

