3.2.2.1.6 Progression Free Survival

PFS is defined as the time from first dose of Cycle 1 until the date of objective disease progression or death (by any cause in the absence of progression) regardless of whether the patient withdraws from study therapy or receives another anti-cancer therapy prior to progression (i.e. date of PFS event or censoring – date of first dose + 1). Patients who have not progressed or died at the time of analysis will be censored at the time of the latest date of assessment from their last evaluable RECIST assessment. However, if the patient progresses or dies after two or more missed visits, the patient will be censored at the time of the latest evaluable RECIST 1.1 assessment prior to the two missed visits.

If the patient has no evaluable post-baseline visits or does not have baseline data they will be censored at Day 1 unless they die within 2 visits of baseline (16 weeks plus 1 week allowing for a late assessment within the visit window).

The PFS time will always be derived based on scan/assessment dates, not visit dates.

RECIST assessments/scans contributing towards a particular visit may be performed on different dates.

The following rules will be applied:

- For investigational assessments, the date of progression will be determined based on the earliest of the dates of the component that triggered the progression
- When censoring a patient for PFS the patient will be censored at the latest of the dates contributing to a particular overall visit assessment

Note: for TLs only the latest scan date is recorded out of all scans performed at that assessment for the TLs and similarly for NTLs only the latest scan date is recorded out of all scans performed at that assessment for the NTLs.

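### For progressions first judged equivocal and confirmed later, the protocol dates the event at the initial scan but the SAP derivation dates it at the confirming scan

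*Protocol*

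**What the plan says.** **Protocol.** Section 8.1.2 covers the case "If the Investigator is in doubt as to whether progression has occurred, particularly with response to NTLs or the appearance of a new lesion" and advises continuing treatment until reassessment at the next scheduled scan, or sooner if clinically indicated. It then fixes the date: "If repeated scans confirm progression, then the date of the initial scan should be declared as the date of progression". The efficacy-analysis section (9.4.1) has the same rule for later reassessment: "the date of the initial scan should be declared as the date of progression if the repeat scans confirm progression". Appendix H, under New Lesions, applies it to an equivocal new lesion: "If repeat scans confirm there is a new lesion, then the progression date should be declared using the date of the initial scan".

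**SAP.** Section 3.2.2.1.1 states: "RECIST outcomes (i.e. PFS, ORR etc.) will be calculated programmatically for the site investigator data from the overall visit responses". The same section carries over the Appendix H requirement, "The finding of a new lesion should be unequivocal", but not the Appendix H sentence on dating an equivocal lesion that is later confirmed. New lesions are captured as Yes or No. The non-target categories are CR, PD, Non-CR/Non-PD, NE and NA, with none for an equivocal finding. Section 3.2.2.1.6 gives the date rule: "For investigational assessments, the date of progression will be determined based on the earliest of the dates of the component that triggered the progression". Section 3.2.2.1.4 ties the end of response to the PFS date. Section 6, which lists changes from the protocol, covers PK parameters only.

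**The concern.** The protocol treats the confirming scan as evidence about the initial scan and moves the event back. The SAP program sees only what each visit records. If the first visit is recorded as SD or PR because the finding was in doubt, the first PD it meets is at the confirming visit. In any affected patient the error runs one way, towards a later progression date.

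At stake are PFS, duration of response, best objective response and ORR. All are secondary, but SAP Section 1.1 keeps limited efficacy outputs for publication. Section 4.2.2 plans Kaplan-Meier summaries of PFS, progression-free percentages every 3 months and ORR, with 80% intervals. A reader of those outputs would assume the protocol definition was applied.

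**Working it through.** The plan states no figure to reproduce. The check compares the two dating rules and then sizes the difference.

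**1. Does any SAP rule reach back to the earlier visit?** The rule in 3.2.2.1.6 follows a sentence about scans of one visit being done on different dates. It chooses among dates within the visit that triggered PD and does not touch an earlier visit recorded as non-PD. The SAP names no investigator-declared progression date as an input. The modified RECIST text in 3.2.2.1.1 says how to classify an unconfirmed progression but gives no dating rule, and protocol 8.1.2 excludes those criteria for both current modules.

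**2. Case by case.** PFS in days = event date − first dose date + 1 (SAP 3.2.2.1.6).

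| Recorded history | Protocol | SAP | Shift |
|---|---|---|---|
| Target-lesion PD, unequivocal non-target PD or ticked new lesion at week 16 | 16×7+1 = 113 | 113 | 0 |
| Equivocal at week 16, recorded non-PD; PD at week 24; week 16 left unchanged | 113 | 24×7+1 = 169 | 56 days |
| As above, but the site later enters the finding at week 16 | 113 | 113 | 0 |

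Using the SAP month of 30.4375 days, 56/30.4375 = 1.84 months.

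**3. Range of the gap.** Scans are every 8 weeks ±1 week. A confirming scan comes at least 4 weeks after the prior one, preferably at the next scheduled visit (protocol 8.1.1). At the next visit the gap is 8 weeks, or 6 to 10 with both windows at their extremes. The overall range is 4 to 10 weeks (28 to 70 days).

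**4. Average over all progressors.** Mean shift = f × gap, where f is the share of progressions first recorded as non-PD and left so. The documents do not give f. With an 8-week gap:
- f = 5%: 0.4 weeks
- f = 10%: 0.8 weeks
- f = 20%: 1.6 weeks
- f = 30%: 2.4 weeks

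**5. The 3-month percentage, for illustration.** Three months is 3×30.4375 = 91.3 days, about 13.0 weeks. A week-8 finding confirmed at week 16 (day 113) moves past it; one confirmed at week 12 (day 85) does not. Assume exponential progression with a median of 15.9 weeks (protocol 11.2.1.2: PLD in refractory ovarian cancer, not this population) and confirmation always at the next scheduled scan. The proportion progressing by week 8 is 1 − 2^(−8/15.9) = 0.294. The 3-month figure rises by 0.294×f: from 70.6% by 2.9 points at f = 10%, or by 8.8 points at f = 30%. Simulation of the same set-up agrees to about 0.1 point. If all confirmations came at 4 weeks, the rise would be zero.

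**6. Response endpoints.**
- *ORR.* Take PR at week 8, PR with an equivocal new lesion at week 16 (recorded PR), and PD at week 24. The SAP counts a confirmed response of (24−8)×7+1 = 113 days. With backdating, week 16 is PD, the PR is unconfirmed and the patient is not a responder. One such patient is 33.3 points of ORR in a cohort of 3, 16.7 in 6 and 3.3 in 30.
- *Best objective response.* A week-8 finding recorded as SD and confirmed at week 16 gives SD under the SAP and PD with backdating.
- *Duration in a true responder.* PR at weeks 8 and 16, an equivocal lesion at week 24 and PD at week 32 give (32−8)×7+1 = 169 days under the SAP, against 113 with backdating.

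**The case against.** The strongest reply is that SAP silence need not be a contradiction. The protocol also assigns visit responses by program, in the same Section 9.4.1 that states the backdating rule. Its instruction to declare the initial date is addressed to the site. A site that enters the confirmed lesion or non-target progression at the initial scan will get the initial date from the SAP program. The eCRF, which might settle this, is not among the documents. Further, protocol 9.4.1 assesses Part A efficacy by ORR and keeps the full set of endpoints for Part B, which the SAP has dropped. No hypothesis is tested and development has been halted.

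Much of this stands. The effect disappears where sites recode, and the consequences are limited to descriptive summaries. But declaring a date is not the same as being told to change an earlier visit record; no passage gives that second instruction, and the SAP takes no declared date as input. The result therefore depends on unspecified data entry that may differ between sites. The SAP does plan PFS and duration of response for Part A.

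A reader might infer that PFS and duration of response are overstated by a scan interval across the trial. The documents do not support that. Under SAP 3.2.2.1.1 a first recorded PD counts at once, without confirmation, so most routes to progression carry the same date under both documents. Nor can the 3-month percentages above be read as estimates of bias: they rest on an assumed share, a borrowed median and confirmation at the next scheduled scan.

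**Conclusion.** The inconsistency is real but narrow. It concerns progressions first judged equivocal, mainly non-target change or a possible new lesion, that were recorded as non-PD, confirmed later and not recoded. For these the SAP departs from the protocol's stated date without declaring it. PFS, and duration of response in responders, are then longer by about 8 weeks (4 to 10), and the specific visit sequence shown above turns a non-responder into a confirmed responder. How often either happens cannot be judged from the documents. The point deserves correction because the error is one-directional, a single patient matters in cohorts of this size, and the remedy is small. It does not affect safety conclusions or any decision rule in the current SAP.

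**What to change.** Add to SAP 3.2.2.1.6, and apply to BoR, ORR and DoR: when a later scan confirms an earlier equivocal non-target progression or new lesion, the overall visit response at the first scan showing it is set to PD, and that scan's date is the progression date. Say how such cases are found: from the eCRF if it captures them; otherwise by a data query, before database lock, asking the site to update the earlier visit's new-lesion or non-target entry.

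If the sponsor prefers to keep the later date, declare the departure from protocol 8.1.2, 9.4.1 and Appendix H in SAP Section 6.

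The cost is one derivation rule, some query work if the eCRF has no suitable field, and slightly less favourable figures where cases exist. No additional scans or patients are needed.
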